The primary aim is to determine the efficacy of training with this exoskeleton and its ability to improve transfers to standing and sitting as assessed by the five times sit-to-stand test. A secondary aim will be to assess effects of the device during overground ambulation. Outcome measurements to investigate changes of knee range of motion and loading of the paretic limb will be accomplished using an instrumented goniometer; changes in limb loading will be monitored using a foot pressure mapping system; and stepping parameters will be recorded using the GaitRite carpet. An exploratory outcome of changes in energy expenditure during ambulation with and without the powered exoskeleton will be assessed from a 6-minute walking test using a portable metabolic cart. Another exploratory outcome measures of QOL will be determined using the SF-36 and

the Stroke Specific Quality of Life Scale. Additional exploratory outcomes to measure body composition, bone mineral density changes will be assessed using Dual X-ray Absorptiometry (DXA). Additional exploratory outcomes include measuring changes in cortical, corticospinal and spinal excitability in response to brain, spinal and peripheral nerve stimulation (PNS), and brain activation using electroencephalogram (EEG).

Baseline testing for both groups will be performed while ambulating without the device and prior to starting in the training program. The exoskeleton group will repeat testing within the first 3 sessions of the training program. Mid-point assessments will be obtained after 12 and 24 sessions of training. Post assessments will be obtained after 36 sessions of training. Retention will be assessed by repeating the assessments without the exoskeleton after 1 month of stopping the training program.

It is anticipated that longitudinal training with the device will increase number of squats achievable, increase knee flexion during swing, increase loading of the paretic limb, and induce symmetrical stepping. No immediate effect on energy expenditure by the device is expected however, a training effect is expected to demonstrate improvement in the energy cost of ambulation. Any gains observed during this study may not be retained, but as this device has the potential to be used in the home and community environment, justifying a prescription of this device for retention purposes may be warranted. Use of this device may also lead to improvement of QOL.

2. Specific Aims

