The 5xSTS test will be used to address the primary aim of improving participants' squatting ability (LE Strength) (33). This test is performed using a standard free-standing chair with a straight back, solid seat and a seat height of 17 inches. Participants will be instructed with the following statement "By the count of 3, please stand up and sit down as quickly as possible for 5 times. Place your hands on your lap and do not use them throughout the procedure. Lean your back against the chair's backrest at the end of every repetition." The time to complete the test will be recorded and will start once the person back leaves the back rest and stops once the back touches the back rest for the 5th time.

Assessment of gait changes will be performed using the GaitRite Carpet (CIR Systems Inc), the F-scan foot pressure system (Tekscan) and the instrumented goniometer (bendlabs). These measurements will be performed with and without the device. The GaitRite measurement will be obtained by asking each participant to walk over a carpet equipped with sensors, which provide information regarding cadence, step length and time spent on each foot. The F-Scan foot pressure system requires the participant to walk with a disposable insole, which is cut to fit inside their shoe. The disposable insole contains an array of sensors, which provide a continuous pressure profile of each foot during ambulation. This system will measure the percentage of total body weight loaded during the different segments of the stance phase (heel-strike, stance and toe-off) as well as Protocol ASS-20-01

MIRB# 01929

Table 2: Timeline for testing and training

Week:	Schedule of Procedures and Testing									
	-2 to -1	-1	1-4	4-5	5-8	8-9	9-12	12-13	16	
Phase	Pre Screen	Screening /Baseline Testing	Training	Assessments	Training	Assessments	Training	Post Assessments	1-Month Follow-up	
Chart reviews	x									
Consent	x									
Medical History/ Demographics		x								
Fugl-Meyer		x		x		x		x		x
EEG	x		x					x		x
Neuronal Excitability		x						x		x
DXA	x							x		
QOL(SF36 and SSQOL)		x						x		
Training session number			1-3	3-12		12-24		24-36		
Assessments with out Keeogo (both Control and Exoskeleton group)										
5xSTS	x	d	d	x	d	x	d	x		x
Gaitrite	x	w	w	x	w	x	w	x		x
F-Scan	x			x		x		x		x
Energy Expenditure	x			x		x		x		x
Knee range while walking	x	w	w	x	w	x	w	x		x
10mWT	x	d	d	x	d	x	d	x		x
TUG	x	w	w	x	w	x	w	x		x
6MWT	x	d	d	x	d	x	d	x		x
Assessments with Keeogo (only Exoskeleton Group)										

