5xSTS		d	d	x	d	x	d	x		
Gaitrite		w	w	x	w	x	w	x		
F-Scan	x		x			x		x		
Energy Expenditure		x		x		x		x		
Knee range while walking		w	w	x	w	x	w	x		
10mWT		d	d	x	d	x	d	x		
TUG		w	w	x	w	x	w	x		
6MWT		d	d	x	d	x	d	x		

Key: w=weekly; d=daily; x=once

during the entire gait cycle for each lower extremity. An electronic goniometer will be strapped to each lower extremity for independent and simultaneous measurement and recording of knee ROM.

Testing sessions to assess energy expenditure will be performed. Participants will be asked to wear a face mask attached to a portable metabolic cart (Oxycon Mobile, Vyaire Medical Inc.). Measurements of oxygen uptake (VO_2), heart rate (HR) and respiratory rate (RR) will be assessed and recorded. These measurements will be acquired during 6 minutes of quiet sitting (rest) followed by ambulating at a comfortable, self-selected pace for 6 minutes.

The Fugl-Meyer Assessment Lower Extremity (FMA-LE) will be used as a general score of lower extremity motor and sensory function/post-stroke recovery (34). General changes in QOL will be assessed using the SF36 (35) and SSQOL scales (36).

A Dual X-Ray Absorptiometry (DXA) will be used to determine changes in body composition and bone density. A scan of the total body will be used to view changes in bone mineral content (BMC), lean mass, and fat mass. Scans of both hips, and both knees will be used to compare bone mineral density (BMD).

Motor responses will be measured using surface electrodes placed on the participants skin over key muscles to determine changes in cortical, corticospinal and spinal excitability. These responses will be brought about using either transcranial magnetic stimulation (TMS), transcutaneous spinal cord stimulation (TSCS) or PNS. TMS uses electromagnetic pulses, while TSCS and PNS use a series of electrical pulses. Whether it is stimulation over the brain, spine or peripheral nerve, stimulation causes the targeted muscles to twitch. These twitches are then recorded and compared.

EEG will be used to measure changes in brain activation. A 64 electrode EEG cap will be placed on the subjects head and will record brain activity during a resting state.

Description of Data and Statistical Analyses

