The loading profile obtained from the F-Scan foot pressure system will be normalized over the gait cycle as percentage of gait cycle and percentage of body weight for each foot. The total area under the curve will be calculated to obtain a total load on each lower extremity. Peak measurements from heel strike and toe-off will be calculated from the curve along with mid stance where load is typically diminished. Maximum knee flexion angles from 10 continuous steps will be averaged for each limb.

Metabolic measurements (VO_2 , HR and RR) will be recorded as averages every minute. Energy cost of distance travelled will be calculated by dividing VO_2 normalized to body weight (ml/kg/min) by the distance traveled (ml/kg/m). The 6 values from the consecutive 1-minute recordings will be averaged for sitting and walking conditions.

Descriptive statistics will be employed for demographic and Fugl-Meyer data. A single group, repeated measures design will be employed in the experimental group to test the within-group effect of using the powered exoskeleton. A two group repeated measures design will be employed to test the between-group differences in outcomes. All outcome measurements will be analyzed using a mixed model ANOVA to determine significant main and interaction effects of group (control, experimental) and time (baseline, session 36, 1-month follow-up). A similar mixed model ANOVA will be used to determine significant main and interaction effects of the two conditions (without [w/o] and with [W] Keeogo exoskeleton) in the experimental group for the 3 time points (baseline, session 36, 1-month follow-up). Post hoc analyses of significant data will be performed using t-tests.

Table 3: Timeline of activities to complete the study

TIME LINE	Year 1				Year 2			
	Q1	Q2	Q3	Q4	Q1	Q2	Q3	Q4
Start-up Activities								
IRB & R&D	x				x			x
Staff Hiring and Training	x							
Purchase Equipment	x							
Database development	x							
Participant Screening	x	x	x	x	x	x		
Participant Enrollment	3	4	4	3	1	0		
Database management	x	x	x	x	x	x		
Abstract writing				x	x	x		
Manuscript writing					x	x		

Potential Difficulties and Limitations

The greatest hurdle in conducting investigations with devices is recruiting participants and completing the training as well as obtaining regulatory approval to conduct the study. Feasibility to enroll and complete the 15 participants is

Protocol ASS-20-01

MIRB# 01929

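### The energy-cost formula cannot give its stated unit: VO2 per minute divided by a distance is not ml/kg/m, and taken literally over a 6-minute walk it gives one sixth of the cost per metre

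*Combined protocol and SAP*

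**What the plan says.** Three consecutive sentences under Description of Data and Statistical Analyses govern the metabolic outcome.

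- Recording: "Metabolic measurements (VO_2 , HR and RR) will be recorded as averages every minute".
- Energy cost: "Energy cost of distance travelled will be calculated by dividing VO_2 normalized to body weight (ml/kg/min) by the distance traveled (ml/kg/m", where the closing bracket is the unit of the result.
- Averaging: "The 6 values from the consecutive 1-minute recordings will be averaged for sitting and walking conditions".

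Under Outcome Measurements and Testing sessions, the test is described thus: "These measurements will be acquired during 6 minutes of quiet sitting (rest) followed by ambulating at a comfortable, self-selected pace for 6 minutes". The text on the secondary energy-expenditure aim in Specific Aims also gives a 6-minute period, and the opening summary says the measure "will be assessed from a 6-minute walking test using a portable metabolic cart". The list of abbreviations defines m as meter and min as minute, so the result is meant to be per metre. The outcome is not primary: the summary calls it exploratory and Specific Aims calls it secondary.

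**The concern.** The sentence gives an operation and a unit, and the two do not agree. It states no time term: the divisor is not called a speed or a per-minute distance, and VO2 is not multiplied by walking time. In ordinary use, the distance travelled in a 6-minute walk is its total distance. An analyst who divides mean VO2 by that total and copies the printed unit will report values that are too small by the number of minutes walked.

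What is at stake is the reported level of energy cost and any comparison with figures from elsewhere. The Background section itself relies on such a comparison: it states that walking without a device after stroke costs twice as much energy as in able-bodied controls. A sixfold scale error would turn a true ratio of 2 into 2/6, or one third, if the outside figure were in correct units.

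**Working it through.** **Inputs**

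- Formula and result unit: Description of Data and Statistical Analyses.
- Walk duration, 6 minutes: Outcome Measurements and Testing sessions, and Specific Aims.
- Walking speed, 0.15 to 0.75 m/s: inclusion criterion 3. The midpoint is (0.15 + 0.75)/2 = 0.45 m/s.
- Walking VO2, 11.2 ml/kg/min: an assumption to show scale. It comes from the spinal cord injury exoskeleton work in Preliminary Studies; the plan gives no value for stroke.

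**Step 1. Can the stated unit be reproduced?**

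- Literal: (ml/kg/min) / m = ml/kg per minute per metre. This is not the stated unit.
- Divide by speed: (ml/kg/min) / (m/min) = ml/kg/m. This agrees.
- Total oxygen over total distance: (ml/kg/min × min) / m = ml/kg/m. This agrees.
- Each minute's VO2 over that minute's metres, then averaged: ml/kg/m. This agrees, but the text does not state per-minute distances.

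**Step 2. Size of the discrepancy.** Metres per minute = speed × 60; metres in 6 minutes = speed × 360.

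| Speed (m/s) | m per min | m in 6 min | VO2 / speed (ml/kg/m) | VO2 / total distance (literal) |
|---|---|---|---|---|
| 0.15 | 9 | 54 | 11.2/9 = 1.244 | 11.2/54 = 0.207 |
| 0.45 | 27 | 162 | 11.2/27 = 0.415 | 11.2/162 = 0.069 |
| 0.75 | 45 | 270 | 11.2/45 = 0.249 | 11.2/270 = 0.041 |

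Total oxygen is 11.2 × 6 = 67.2 ml/kg. Over the total distance this gives 67.2/54 = 1.244, 67.2/162 = 0.415 and 67.2/270 = 0.249, the same as dividing by speed. The ratio of the last two columns is 6 in every row because it is the walk duration. It does not depend on the assumed VO2: at 0.45 m/s, a VO2 of 8 gives 0.296 against 0.049, and a VO2 of 14 gives 0.519 against 0.086.

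**Step 3. Effect on the planned tests.** If every walk lasts 6 minutes, each literal value is the correct value times 1/6. Means, differences and standard deviations all shrink by the same factor, so F and t statistics, p-values and percent changes are unchanged. Multiplying by 6 recovers the correct values.

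**Step 4. Do the unit-correct forms differ from each other?** At steady speed they are identical. With VO2 held at 11.2 and per-minute speed falling evenly from 0.50 to 0.40 m/s (assumed), the mean of six per-minute ratios is 0.417 against 67.2/162 = 0.415, or +0.6%. From 0.60 to 0.30 m/s (assumed), it is 0.439 against 0.415, or +5.7%. This is small beside a factor of 6, but it is a reason to name one form.

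**The case against.** The strongest reply is that the intended quantity can be inferred. The result unit is printed. Only a divisor per minute, or a numerator multiplied by time, satisfies it, so anyone who divides by the total distance must overlook the unit. The neighbouring sentences work in one-minute values, which makes one minute the natural time base. This stands as to likelihood: the unit-consistent reading is the more probable one. It does not make the sentence right. The averaging sentence covers sitting as well as walking, so it does not by itself show that VO2 is paired with each minute's metres, and nothing else supplies the missing time term.

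A reader might also infer more than the documents support.

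- *That distance is not collected in the metabolic test*, because the description says "Measurements of oxygen uptake (VO_2), heart rate (HR) and respiratory rate (RR) will be assessed and recorded" without mentioning distance, and because Table 2 lists "Energy Expenditure" and the 6-minute walk test on separate rows. This does not follow. The formula itself requires the distance, and the summary takes the measure from a 6-minute walking test. The separate rows can be explained by frequency: the walk test also has daily entries, while energy expenditure has only single ones.
- *That comparisons are biased by unequal walking times.* The literal index would vary with duration, but both descriptions of the test fix the walk at 6 minutes, and nothing in the documents shows that durations will differ.
- *That the planned tests are invalid.* They are not, since a constant factor leaves them unchanged.

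**Conclusion.** The formula is wrong as written, and the point is minor. The unit mismatch is certain, because it needs no assumption beyond the plan's own units. The sixfold understatement is conditional: it arises if the literal formula is applied with the total distance of a full 6-minute walk, which is the less likely reading. In that case, absolute energy-cost values and comparisons with outside ml/kg/m figures would be wrong by a factor of 6. The group, time and device tests and percent changes would not be affected, provided that every walk lasts 6 minutes and one rule is used throughout. VO2, heart rate and respiratory rate as outcomes are untouched. The ml/kg/m figures shown rest on a VO2 borrowed from another population; the factor itself does not.

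**What to change.** Replace the sentence with a definition whose units close: energy cost (ml/kg/m) = mean walking VO2 (ml/kg/min) divided by mean walking speed (m/min) over the same interval. Add that this equals total oxygen uptake (ml/kg) divided by total distance (m), and that the same formula applies at every visit and in both device conditions.

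The cost is one line of analysis text. It needs no new visit, no additional participants and no change of design, and the only inputs are VO2, distance and walking time, which the plan already calls for or fixes. If any values have already been computed as VO2 over total 6-minute distance, multiplying them by 6 corrects them.

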The 5xSTS is used to determine leg power and an aspect of transfer skill. This test will be used to assess a level of improved function while wearing the device. It will also be used to determine if any training effect is observed after 3 months (36 sessions) of training when not wearing the device.

Secondary Aim: To determine the efficacy of ambulation training using a powered orthotic exoskeleton on knee ROM and loading of the paretic LE while ambulating over ground with and without the device for 3 months (36 sessions).

Multiple outcome measures will be used to determine the effect of the powered exoskeleton on a person's gait biomechanics and functional competency. An instrumented goniometer will record knee joint angles during multiple gait cycles to assess changes in knee flexion during the swing phase. Because the powered orthotic exoskeleton provides stability during the stance phase, stepping parameters will be assessed using an instrumented carpet to determine if the paretic limb has more equitable and symmetrical load.

Secondary Aim: To determine the energy expenditure of ambulation with and without the powered orthotic exoskeleton at baseline and 3 months (36 sessions) post training.

A portable metabolic cart will assess oxygen consumption during the two ambulation conditions (i.e., with and without the device) over a 6-minute period. It is anticipated that the baseline comparison test will not show any metabolic changes due to the added weight of the device and negate any metabolic benefit from the motors powering the knee joint movement. However, a training effect over the 3 months (36 sessions) compared to baseline is anticipated due to the participant becoming more comfortable with the device, thus using the paretic LE more effectively.

Exploratory Aim: To determine the retained function (squatting, knee ROM, paretic LE loading and energy expenditure) 1-month post cessation of training without the device.

It is not known whether any benefits from training will be retained, but if benefits exist while wearing the device, but are not retained, then long term use may be indicated.

Exploratory Aim: To determine differences in QOL measurements (SF36 and Stroke Specific Quality of Life Scale [SS-QOL]) over 3 months (36 sessions).

The mobility portions of the SSQOL and SF36 will be used to determine whether changes in ambulation affect QOL in persons post stroke.

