Eight participants participated in oxygen uptake (VO_2) measurement after 40 training sessions using a powered exoskeleton (ReWalk) (2). Each participant was asked to wear a mask attached to a portable metabolic system (Oxycon Mobile; Jaeger, Germany) and a 12-lead electrocardiogram that determined VO_2 and heart rate (HR) over one-minute intervals. These measurements were recorded during three phases: 6-minutes of sitting, 6-minutes of standing and 6-minutes of walking. Data within each phase were averaged and analyzed to reveal a significant increase ($p < 0.001$) in VO_2 response (Figure 2) during walking (11.2 ± 1.7 mL/kg/min) compared to

Protocol ASS-20-01

MIRB# 01929

[figure not shown]

Figure 1: Vertical ground reaction force indexed: heel strike vertical ground reaction force (vGRG_{HS}), mid-stance vertical ground reaction force (vGRG_{MS}) and toe-off vertical ground reaction force (vGRF_{TOAB} and vGRF_{TOSCI}) (3).

sitting (3.5 ± 0.4 mL/kg/min) and standing (4.3 ± 0.9 mL/kg/min). A similar response was observed in HR values (Figure 3) with a significant increase ($p < 0.001$) observed during walking (118 ± 21 beats per min (bpm)) compared to sitting (70 ± 10 bpm) and standing (81 ± 12 bpm). Prior to this work, many would hypothesize that ambulating with a device providing total assistance of leg movement would not result in a significant increase in energy expenditure, but this was not the case. Similar results have been shown with the Indego (5) and the Ekso (29) exoskeletons, which support that routine ambulation, at this level of VO₂ and HR has the potential to decrease adiposity and other associated health-related consequences of paralysis. This work has not been performed using the Keeogo, but as it requires active user input at the knee joint, the user should also an elevated VO₂ and HR which may lead to a similar response.

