This study will recruit 15 people with chronic and stable stroke (>6 months) who are interested in ambulation training using a powered exoskeleton. This study will be conducted at the James J. Peters VA Medical Center (JJPVAMC) therefore recruitment training and testing in this project will require participants to travel to this medical center in the Bronx, NY. The following criteria will be employed for participation:

Inclusion Criteria:

1. Males and females between 18 and 89 years old;
2. Hemiplegia or hemiparesis due to stroke (>6 months);
3. Able to walk between 0.15-0.75m/s
4. Self-reported limitations to mobility and walking activities due to paretic side knee stiffness and loss of range of motion;
5. Weight under 250lbs
6. Desire to increase daily activity levels; and
7. Able and willing to commit to participation and follow directions and communicate basic needs.

Exclusion criteria:

1. Neurological paralysis causing an inability to stand, weight bear or take stepping movements;
2. Fixed contractures resulting in limited range of motion in the hip, knees, or ankles that prevent sitting, standing, walking, and/or squatting activities;
3. Modified Ashworth Scale for spasticity greater than 3 in the lower limbs
4. Able to walk at a normal walking speed (1.4 m/s, 3.2 mph) or better during the 6MWT;
5. Anthropometric incompatibility with the device
 - a. Femur length less than 36 cm or greater than 45 cm;
 - b. Upper thigh circumference less than 55 cm or greater than 75 cm;

- c. Lower thigh circumference less than 27 cm or greater than 40 cm;
- d. Calf circumference less than 33 cm or greater than 49 cm;
- e. Ankle circumference less than 27 cm or greater than 40 cm;
- f. Shin length less than 26 cm;
- g. Waist circumference less than 71 cm or greater than 107 cm;
- 6. Any medical complication or co-morbidity as judged by the study physician to be contraindicated for wearing the device or walking (e.g., cardiovascular disorders, pressure ulcers, open wounds, lower limb vascular disorders, or other medical conditions); and
- 7. Pregnant or planning to become pregnant (Female participants).

A subset of participants will have MEP recordings using as a result of PNS, TSCS and TMS. The inclusion criteria is the same as previously described. The following is the additional exclusion criteria.

Exclusion criteria:

- 1. History of seizures, brain tumor, brain surgery, or brain abscess;

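### Energy cost per metre has no resting term and pace is free, so a change in it cannot by itself show better walking economy; net cost should be reported with gross cost and speed

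*Combined protocol and SAP*

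**What the plan says.** Under Outcome Measurements and Testing sessions, the energy test is described as follows: "These measurements will be acquired during 6 minutes of quiet sitting (rest) followed by ambulating at a comfortable, self-selected pace for 6 minutes". Speed is neither fixed nor matched between visits or conditions.

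Description of Data and Statistical Analyses then defines the outcome: "Energy cost of distance travelled will be calculated by dividing VO_2 normalized to body weight (ml/kg/min) by the distance traveled (ml/kg/m". It adds: "The 6 values from the consecutive 1-minute recordings will be averaged for sitting and walking conditions". The sitting mean is given no further use. The mixed model ANOVA names group and time, and device condition within the exoskeleton group. It names no speed covariate.

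Specific Aims makes this a secondary aim: "Secondary Aim: To determine the energy expenditure of ambulation with and without the powered orthotic exoskeleton at baseline and 3 months". The opening summary lists it as exploratory. The expected result is stated twice. The opening summary says that "a training effect is expected to demonstrate improvement in the energy cost of ambulation". Specific Aims says: "However, a training effect over the 3 months (36 sessions) compared to baseline is anticipated due to the participant becoming more comfortable with the device", and goes on to link this to better use of the paretic leg.

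**The concern.** Oxygen used at rest accrues per minute. Expressed per metre, it equals resting VO2 divided by speed, so it shrinks when a person speeds up and grows when a person slows down, even if the cost of moving the body is unchanged. Gross cost per metre carries this component.

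Speed may well differ across the contrasts of interest. Background and Significance cites improved walking speed after task training of the kind used here, and the device weighs about 15 lb, so pace may also differ with and without it. A fall in gross cost could then reflect faster walking, better economy, or both. This matters because the aims attach an economy mechanism to the result, and the pilot is meant to inform the design of later studies.

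**Working it through.** **Inputs**
- Sitting and standing VO2: "sitting (3.5 ± 0.4 mL/kg/min) and standing (4.3 ± 0.9 mL/kg/min"; walking VO2 11.2 mL/kg/min. These come from Preliminary Studies: eight participants with spinal cord injury in a different exoskeleton. Using them for stroke is an assumption.
- Speed at entry, from Inclusion Criteria: "Able to walk between 0.15-0.75m/s", which is 9 to 45 m/min.
- Locomotor cost c: not given in the documents. Assumed 0.1, 0.2 and 0.3 ml/kg/m.

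The plan gives no expected energy cost and no expected speed change, so there is no figure to reproduce.

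**Formulas** (v in m/min, R = VO2 at zero speed, S = sitting VO2)
- Walking VO2 = R + c·v
- Gross cost = R/v + c
- Net cost = (walking VO2 − S)/v = (R − S)/v + c

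**Step 1: resting part of gross cost, R = 3.5.** At 0.15 m/s it is 3.5/9 = 0.389 ml/kg/m, at 0.40 m/s 3.5/24 = 0.146, and at 0.75 m/s 3.5/45 = 0.078. That is a five-fold range across eligible speeds.

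**Step 2: walking VO2 of 11.2 at the starting speed, net cost per metre then held constant.** Gross cost after the change is (11.2 − 3.5)/v0 + 3.5/v1, so the relative change is −(3.5/11.2)(1 − v0/v1) = −0.3125(1 − v0/v1).

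| Speed (m/s) | Gross cost (ml/kg/m) | Change |
|---|---|---|
| 0.15 to 0.25 | 1.244 to 1.089 | −12.5% |
| 0.40 to 0.50 | 0.4667 to 0.4375 | −6.25% |
| 0.65 to 0.75 | 0.2872 to 0.2752 | −4.2% |
| 0.40 to 0.30 | 0.4667 to 0.5153 | +10.4% |

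**Step 3: fixed c in place of a fixed starting VO2, R = S = 3.5.** Change in gross cost:

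| Speed (m/s) | c = 0.1 | c = 0.2 | c = 0.3 |
|---|---|---|---|
| 0.15 to 0.25 | −31.8% | −26.4% | −22.6% |
| 0.40 to 0.50 | −11.9% | −8.4% | −6.5% |
| 0.65 to 0.75 | −6.3% | −4.1% | −3.1% |
| 0.50 to 0.40 | +13.5% | +9.2% | +7.0% |

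Steps 2 and 3 differ most at slow speeds. Step 2 implies a different net cost at each starting speed (7.7/9 = 0.856, 7.7/24 = 0.321 and 7.7/39 = 0.197 ml/kg/m), whereas step 3 holds it at the same value throughout.

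**Step 4: how much of this net cost removes.** If R = S, net cost equals c and does not move with speed. That follows from the assumption and is not a finding. If zero-speed cost is instead the standing value, R = 4.3, then net cost = 0.8/v + c and part of the effect stays:

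| Speed (m/s) | Measure | c = 0.1 | c = 0.2 | c = 0.3 |
|---|---|---|---|---|
| 0.40 to 0.50 | Gross | −12.8% | −9.5% | −7.5% |
| 0.40 to 0.50 | Net | −5.0% | −2.9% | −2.0% |
| 0.15 to 0.25 | Gross | −33.1% | −28.2% | −24.6% |
| 0.15 to 0.25 | Net | −18.8% | −12.3% | −9.1% |

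**Step 5: units.** A rate in ml/kg/min divided by metres is not ml/kg/m; the divisor has to be speed. Taken literally with the six-minute distance, the value is six times too small (0.058 against 0.346 at 0.40 m/s with c = 0.2). This is a separate matter and leaves the percentages above unchanged.

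**The case against.** Gross cost per metre is a legitimate quantity. It answers how much oxygen a person spends to cover a distance, and someone who spends less because they walk faster has a practical gain. This stands: a reader might infer that the formula is wrong for the aim, and the documents do not support that.

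A reader might also infer that the plan treats a fall in energy cost as proof of better paretic-leg use. It does not. Specific Aims states an expected mechanism, not a rule of inference, and limb use is measured directly by foot pressure, knee goniometer and instrumented carpet.

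Speed is not hidden either. The energy test itself yields distance, and Table 2 schedules the 10mWT and 6MWT at each main assessment. However, the plan does not say that speed will be read alongside energy cost, and the model does not use it.

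That the sitting value is never subtracted is read from silence, since the plan uses neither the word gross nor the word net. Even so, the one formula given has no resting term, and leaving the choice open allows it to be made after the data are seen.

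Finally, the percentages rest on borrowed values and an assumed locomotor cost. This is true of their size but not of their direction.

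**Conclusion.** The point holds in a limited form. As defined, energy cost moves with walking speed alone, so a change in it cannot by itself support the economy mechanism that the aims anticipate, over time or between device conditions. With constant locomotor cost and any positive resting VO2, faster walking always lowers gross cost. The illustrative size is about 4% to 12.5% per 0.10 m/s gain with the spinal cord injury values, and up to about 32% at the slowest speeds under the assumed c.

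The documents do not show that a spurious effect will occur, because they give no expected change in speed. Nor do they show that subtracting sitting VO2 cures the problem: with their own standing value, net cost still falls by 2% to 5% for 0.40 to 0.50 m/s, and by 9% to 19% for 0.15 to 0.25 m/s. This is an inexpensive improvement to a secondary or exploratory outcome in a 15-person pilot. It does not touch the primary aim.

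**What to change.** In Description of Data and Statistical Analyses, add net energy cost for each condition and visit: mean walking VO2 minus mean sitting VO2 from the same test session, divided by walking speed in m/min. Report it with gross cost (using the same divisor, which also settles the units) and walking speed. State that any conclusion about walking economy or more effective use of the paretic leg will rest on net cost read together with speed. State also whether the sitting period is repeated before each walk or shared between the walks with and without the device, since the protocol does not say.

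The cost is a few sentences. No new measurement is needed if one sitting period per session is used. There are two downsides. Error in the sitting mean adds some variance: an error of e shifts net cost by e divided by speed, so it weighs most in the slowest walkers. It is probably small for a six-minute mean, but the documents give no repeat error from which to calculate it. And because zero-speed cost may exceed sitting cost, some dependence on speed may remain, which is why speed must be shown beside it.
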